Statistical Analysis: The primary endpoint will be summarized as the event rate per Subject with a one-sided 95% upper confidence bound using the Exact method. The upper bound will be compared to the performance goal of 9.6%. If this upper bound is less than 9.6%, it is considered that the Apollo™ micro catheter meets the primary objective. Additionally, an interim analysis will be performed when 80 subjects have reached the 30-day follow-up. The interim prediction power will be calculated and the sample size may be adjusted as appropriate. Adverse events for all enrolled Subjects will be collected and reported. For adverse event reporting, which includes the primary and secondary endpoints, the primary analysis will be based on Subject counts (e.g., the number and percentage of Subjects with event among the total number of Subjects). The data will be presented in the format of $p\%$ (x/N) [e], with p and x being the percentage and number of Subjects with events, respectively, N being the sample size of the analysis population, and e being the total number of events occurred in the x Subjects. For example, the data of 3.1% (5/161) [8] indicates that a total of 8 events occurred in 5 Subjects out of a total of 161 Subjects (3.1%). In addition, the data based on device (e.g., the number and percentage of devices with events among the total number of deployed devices) will also be provided.	

PROTOCOL SYNOPSIS

Sponsor: Micro Therapeutics, Inc. d/b/a ev3 Neurovascular [name]	Protocol Number: NV-APL001 Revision: A, 05-Aug-2014 Product: Apollo™ Onyx™ Delivery Micro Catheter Regulatory Class: Class III Development Phase: Phase IV
---------------------------------------------------------------------------------------------------------------	-----------------------------------------------------------------------------------------------------------------------------------------------------------------------------------------------------------

Sample Size Justification:

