The maximum number of Subjects to be enrolled into this clinical investigation is 161 (with 13% attrition included). To establish a safety performance goal for the primary endpoint, literature research was conducted on the reported data of catheter retainment. The table below summarizes the rates from the peer-reviewed literature. The rate ranges from 1% to 9.7% with an un-weighted average rate of 5.8% and weighted average of 5.7%. The one-sided 95% upper confidence interval for the individual studies ranged from 4.6% to 16.3%.

Table 1-1. Event Rate Based on Literature Review

Citation	Purpose	Catheter*	Country	Catheter Retainment Frequency (pts)	One-Sided 95% Upper Bound**
Gao, K et a. Chinese Med J 2009; 122:1851-1856.	Onyx delivery	M, U	China	5/115 = 4.4%	8.9%
Katsaridis, V et al 2008 Neuroradiology 2008; 50: 589-597.	Onyx delivery bAVM	M, U	Greece	1/101 = 1%	4.6%
Mounayer, C et al AJNR 2007; 28: 518-523.	NBCA, Onyx delivery bAVM	F, U	France	4/94 = 4.3%	9.5%
Panagiotopoulos, V et al AJNR 2009; 30: 99-106.	Onyx delivery bAVM	M, U	Germany	1/82 = 1.2%	5.7%
Saatci, I et al J Neurosurg 2011; DOI: 10.3171/2011.2.JNS.09830.	Onyx, NBCA delivery bAVM	F, U, M	Turkey	28/350 = 8.0%	10.8%
Song, D et a. Intervent Neuroradiol 2005; 11 (SUPPL. 1): 179-184.	Onyx delivery BAVM	M, U	China	3/50 = 6.0%	14.8%
Weber et al. AJNR 2007; 28: 371-377.	Onyx Delivery bAVM	U	Germany	9/93 = 9.7%	16.3%
Un-weighted Average					51/885 = 5.8%
Weighted Average					5.7%

Note: Table 1-1 is identical to Table 3 in clinical protocol.

*M = Marathon; U = UltraFlow; E = Echelon; F = FlowRider.

**95% one-sided upper bound is calculated using the Exact method.

The weighted average of catheter retainment event from the table above was used as an estimate of the primary endpoint event rate for this study. Based on a sample size of 161 (maximum sample size), if the event rate is 5.6%, the 95% upper bound is 9.6%. The 5.6% event rate is a conservative estimate calculated by using the weighted average of 5.7% rounded down to account for a whole patient. Based on this upper bound, it is proposed that the performance goal for the primary endpoint be 9.6%. The one-sided 95% upper confidence bound of the observed primary endpoint event rate will be compared to 9.6%. If this upper bound is less than 9.6%, then it is considered that the Apollo™ micro catheter meets the primary endpoint performance goal.

PROTOCOL SYNOPSIS	

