9 STATISTICAL METHODS

9.1 Sample Size and Safety Performance Goal

The maximum number of Subjects to be enrolled into this clinical investigation is 161 (with 13% attrition included). To establish safety performance goal for the primary endpoint, literature research was conducted on the reported data of catheter retention. Table 3 summarizes the rates from the peer-reviewed literature. The rate ranges from 1% to 9.7% with an un-weighted average rate of 5.8% and weighted average of 5.7%. The one-sided 95% upper confidence interval for the individual studies ranged from 4.6% to 16.3%.

Table 3. Event Rate Based on Literature Review

Citation	Purpose	Catheter*	Country	Catheter Retainment Frequency (pts)	One-Sided 95% Upper Bound **
Gao, K et al. Chinese Med J 2009; 122:1851-1856.	Onyx delivery	M, U	China	5/115 = 4.4%	8.9%
Katsaridis, V et al 2008 Neuroradiology 2008; 50: 589-597.	Onyx delivery bAVM	M, U	Greece	1/101 = 1%	4.6%
Mounayer, C et al AJNR 2007; 28: 518-523.	NBCA, Onyx delivery bAVM	F, U	France	4/94 = 4.3%	9.5%
Panagiotopoulos, V et al AJNR 2009; 30: 99-106.	Onyx delivery bAVM	M, U	Germany	1/82 = 1.2%	5.7%
Saatci, I et al J Neurosurg 2011; DOI: 10 3171/2011.2 JNS 09830.	Onyx, NBCA delivery bAVM	F, U, M	Turkey	28/350 = 8.0%	10.8%
Song, D et al. Intervent Neuroradiol 2005; 11 (SUPPL. 1): 179-184.	Onyx delivery BAVM	M, U	China	3/50 = 6.0%	14.8%
Weber et al. AJNR 2007; 28: 371-377.	Onyx Delivery bAVM	U	Germany	9/93 = 9.7%	16.3%
Un-weighted Average					51/885 = 5.8%
Weighted Average					5.7%

*M = Marathon; U = UltraFlow; E = Echelon; F = FlowRider.

**95% one-sided upper bound is calculated using the Exact method.

The weighted average of catheter retention event from the table above was used as an estimate of the primary endpoint event rate for this study. Based on a sample size of 161 (maximum sample size), if

the event rate is 5.6%, the 95% upper bound is 9.6%. The 5.6% event rate is a conservative estimate calculated by using the weighted average of 5.7% rounded down to account for a whole patient.

Based on the one-sided 95% upper-bound it is proposed that the performance goal for the primary endpoint be 9.6%. The one-sided 95% upper confidence bound of the observed primary endpoint event rate will be compared to 9.6%. If this upper bound is less than 9.6%, then it is considered that the Apollo™ micro catheter device meets the primary endpoint performance goal.

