9.2.4 Analysis of Primary Endpoint

The primary endpoint is the composite of any of the following catheter related adverse events:

- Premature (unintentional) catheter tip detachment with clinical sequelae
- Catheter rupture/break/fracture with clinical sequelae
- Retained catheter body in the vasculature

The primary analysis for the primary endpoint is based on Subject counts, not event counts. A Subject with more than one event will be counted only once toward the event rate based on the total number of Subjects with adverse events. An event rate based on event counts will also be presented. For example, if a Subject experiences one "Premature (unintentional) catheter tip detachment with clinical sequelae" and one "Retained catheter body in the vasculature", the Subject will be counted once in the rate of total Subjects with primary endpoint; the same Subject will be counted once in the individual event category of "Premature (unintentional) catheter tip detachment with clinical sequelae" and once in the "Retained catheter body in the vasculature" category.

The primary endpoint will be summarized as the event rate per Subject with a one-sided 95% upper confidence bound using the Exact method. The upper bound will be compared to the performance goal of 9.6%. If this upper bound is less than 9.6%, it is considered that the Apollo™ micro catheter meets the primary objective.

One interim analysis is planned for this study. An interim assessment will be performed when 80 subjects have reached the 30-day follow-up. If the one-sided 96% upper confidence bound is below the pre-specified threshold of 9.6%, the primary safety objective is considered to be met and early trial stop for success will be claimed. On those subjects already enrolled, follow-up will continue according to the protocol. Otherwise, the trial will continue and the final analysis will be performed at the end of study. The 96% confidence level is used for the interim analysis to ensure the overall type I error is controlled at the 0.05 level. In addition, the conditional power will be calculated at the interim analysis to determine if a sample size adjustment is necessary. It will not be necessary to adjust the alpha level if the conditional power is greater than 50% (Chen et al., 2004). However, in case that the conditional power is below 50%, the procedure of Cui et al. (1999) will be followed to ensure the study-wise type I error rate is well controlled.

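### Section 9.2.4 waives the alpha adjustment above 50% conditional power without limiting the direction of the sample-size change, so an unadjusted reduction below 161 can raise the type I error

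*Combined protocol and SAP*

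**What the plan says.** Section 9.2.4 bases success on the "event rate per Subject with a one-sided 95% upper confidence bound using the Exact method", to be compared with the 9.6% performance goal. On timing: "An interim assessment will be performed when 80 subjects have reached the 30-day follow-up". If the one-sided 96% bound is then below 9.6%, the trial stops for success; otherwise it continues. The section says the 96% level is there to hold the overall type I error at 0.05.

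The same paragraph adds a second use of the interim: conditional power is calculated to see whether the sample size needs adjusting. On the error rate it states: "It will not be necessary to adjust the alpha level if the conditional power is greater than 50" per cent. Below 50%, a cited 1999 procedure is to be followed to control the study-wise error.

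The Statistical Analysis entry of the synopsis is looser: "The interim prediction power will be calculated and the sample size may be adjusted as appropriate". Section 9.1 states: "The maximum number of Subjects to be enrolled into this clinical investigation is 161", a figure that includes 13% attrition, and Section 4.2 also says up to 161. Section 9.2.2 bases success on the Full Analysis Set.

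The plan gives no direction of change, no floor or new ceiling, no re-estimation rule, and no event rate for the conditional-power calculation.

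**The concern.** The waiver carries no condition on direction. Its effect differs between increases and reductions, because a reduction gives a favourable first 80 Subjects more weight in the pooled final test than was planned.

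The interim counts covered by the waiver are those that just miss the early stop, which is where a sponsor would have reason to shorten enrolment. At 3 of 80 events the 96% bound is 9.79%, so the trial continues. The 95% bound for the same data is 9.41%, which is below the goal. A short extension tested at an unadjusted 95% could therefore recover part of what the 96% rule withheld. In a single-arm trial the interim count is known, so N could also be chosen knowing which values allow one more event.

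At stake is the promise of 0.05 control. A device whose true rate equals the goal could be declared to have met its safety objective more often than stated.

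**Working it through.** **Inputs.** Goal and null rate 9.6%, one-sided exact 95% final bound, 96% interim bound at n=80 (9.2.4). Maximum 161 including 13% attrition (9.1), so about 0.87 × 161 = 140 evaluable. Design rate 5.6% (9.1). The plan does not say which rate conditional power uses, so both the observed rate and 5.6% are tried.

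**The plan's own figure.** Section 9.1 states: "Based on a sample size of 161 (maximum sample size), if the event rate is 5.6%, the 95% upper bound is 9.6" per cent. The Clopper-Pearson upper bound is the 95% quantile of Beta(x+1, n−x). For x=9, n=161 it is 9.55%, which rounds to 9.6%. Reproduced.

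**Critical counts (upper bound below 9.6%).**
- Interim, 96%, n=80: at most 2 events (2/80 gives 8.01%, 3/80 gives 9.79%).
- Final, 95%: at most 4 at N=93, 5 at N=107, 6 at N=121, 7 at N=140, 9 at N=161.

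**Interim counts inside the waiver (conditional power at 161).**

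| Events of 80 | At observed rate | At 5.6% |
|---|---|---|
| 3 | 0.967 | 0.832 |
| 4 | 0.781 | 0.699 |
| 5 | 0.424 | 0.522 |

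So 3–4 events qualify at the observed rate, and 3–5 at 5.6%.

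**Type I error formula, p = 0.096.**

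P(X80 ≤ 2) + sum over x ≥ 3 of P(X80 = x) × P(Bin(N(x) − 80, p) ≤ c(N(x)) − x)

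Here c(N) is the critical count. N(x) is the reduced N for qualifying counts and 161 otherwise.

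P(X80 ≤ 2) = 0.0141, P(X80 = 3) = 0.03065, P(X80 = 4) = 0.06266, P(X80 = 5) = 0.10114.

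Probability of a false success from each interim count:

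| Events of 80 | N=93 | N=107 | N=121 | N=161 | N=249 |
|---|---|---|---|---|---|
| 3 | 0.641 | 0.513 | 0.437 | 0.330 | 0.244 |
| 4 | 0.269 | 0.254 | 0.233 | 0.199 | 0.166 |
| 5 | 0 | 0.066 | 0.085 | 0.101 | 0.104 |

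Counts of 5 or more, taken to 161, contribute 0.0183 in total. Counts of 6 or more contribute 0.0080.

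- No change: 0.0141 + 0.03065 × 0.330 + 0.06266 × 0.199 + 0.0183 = **0.0549**.
- N=93 at 3–4 events: 0.0141 + 0.03065 × 0.641 + 0.06266 × 0.269 + 0.0183 = **0.0688** (unrounded inputs).
- N=107 at 3–5 events: 0.0141 + 0.03065 × 0.513 + 0.06266 × 0.254 + 0.10114 × 0.066 + 0.0080 = **0.0603** (unrounded inputs).

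**All common reduced Ns, from 81 to one below the maximum.**

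| Analysed maximum, qualifying counts | No change | Range | Above no change | Above 0.05 |
|---|---|---|---|---|
| 161, 3–4 events | 0.0549 | 0.041–0.069 | 26 of 80 | 48 of 80 |
| 161, 3–5 events | 0.0549 | 0.031–0.060 | 10 of 80 | 23 of 80 |
| 140, 3–4 events | 0.0426 | 0.032–0.060 | 34 of 59 | 9 of 59 |

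With 140 analysed, 3–4 events qualify under either rate.

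The pattern is a sawtooth. The error jumps where N first tolerates one more event (93, 107, 121) and falls until the next jump: at 3–4 events, N=106 gives 0.0452 and N=107 gives 0.0639.

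**Increases.** One common N from 162 to 322 in the same zones never exceeds 0.054.

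**The case against.** Four points can be made for the plan.

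- **Direction.** Neither 9.2.4 nor the synopsis mentions a reduction. The only stated route to a smaller trial is the early stop, and asking whether an adjustment is necessary suggests an increase, for which the waiver does no harm here. This stands as a reading of intent. A reader might infer that the sponsor plans to cut enrolment; the documents do not say so. But an increase contradicts the stated maximum, and nothing excludes a reduction.
- **Peaks are not the rule.** A reader might infer that any reduction takes the error to 0.060–0.069. It does not. With 161 analysed and 3–4 qualifying events, 54 of 80 reduced Ns give an error no higher than no change, and the mean is 0.052. This stands, and it limits the claim to what can happen.
- **Part of the excess has another source.** The 0.0549 with no change already exceeds 0.05, because an unadjusted 95% test follows the 96% look. The waiver adds at most 0.0688 − 0.0549 = 0.014 at the worst common N under observed-rate conditional power, and 0.0603 − 0.0549 = 0.005 under 5.6%. This stands.
- **The cited basis.** The 2004 paper behind the waiver is not available here and may set its own limits. If so, 9.2.4 does not carry them over.

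**Conclusion.** The concern holds as a gap in the stated rule. The waiver is unconditional, 161 is the maximum, and a literal reading permits an unadjusted reduction that can take the type I error above both 0.05 and the no-change value.

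The size depends on choices the plan leaves open. With 161 analysed, the peak is about 0.069 (observed-rate conditional power) or 0.060 (5.6%), against 0.055. With 140 analysed, the peak is about 0.060, against 0.043; there more than half of the reduced Ns exceed the no-change value, but only 9 of 59 exceed 0.05.

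These figures assume a true rate of 9.6%, an interim on exactly 80 Subjects, one common reduced N for all qualifying counts, and a pooled 95% exact bound at the end. If N could differ by interim count, the worst case is 0.077, but that needs N=81 at 3 events. At 161 Subjects over 30 months (about 5.4 a month, assumed even), about 85 would be enrolled by the time the 80th reaches 30 days, so that case is not a realistic headline.

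**What to change.** In 9.2.4, state that the sample size will not be reduced after the interim analysis other than by the pre-specified early stop for success, and limit the waiver to cases where conditional power is above 50% and the sample size is not reduced. Put the same limit on the synopsis sentence about adjusting the sample size.

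If the sponsor wants to keep a reduction as an option, apply the error-controlling procedure already named in 9.2.4 to any reduction, whatever the conditional power. In either case, state the event rate used for conditional power.

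The cost is a sentence in each place, with no Subjects beyond the planned 161. The small downside is that the sponsor gives up a free choice to shorten enrolment after a favourable look that misses the early-stop rule. This change does not remove the 0.055 that arises at 161 with no sample-size change.

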9.2.5 Pre-planned Subgroup Analysis

It has been planned to evaluate the primary endpoint in the FAS population using the following subgroups:

- Respective Spetzler-Martin Grades (I-V)
- Subjects where Apollo™ micro catheter tip was surgically resected

- Subjects where the Apollo™ micro catheter tip was not resected
- Centers enrolling small/medium/ large volume of patients

The subgroup analyses are exploratory in nature. No formal statistical hypotheses are proposed. Descriptive statistics will be provided for the subgroup analysis. Event rates based on Subject count and device count will be provided for the subgroups.

9.2.6 Analysis of Secondary Endpoints

For acute and long-term secondary endpoints, descriptive statistics will be provided. Event rates based on Subject count and device count will be provided.

The incidence of catheter and / or tip retention following any deployment of the study device will be summarized using counts, percentages, and 2-sided 95% exact binomial confidence intervals.

Separately, the incidence of catheter and tip retention by the number of deployments of the study device will be summarized using counts, percentages, and 2-sided 95% exact binomial confidence intervals. This tabulation assumes that each procedure / deployment is a separate trial. The intra-subject rate of catheter and tip entrapment will be summarized using descriptive statistics and tabulated by the number of events and the number of deployments.

In order to ensure a sufficient number of cases for long-term follow-up, the expectation is that with 161 subjects enrolled there will be approximately 16 to 26 subjects with 1-year follow-up. The basis of this estimate is that approximately 50% to 80% of the subjects will have the tip retained by design and approximately 20% of these subjects will not undergo surgery and shall be followed for 1-year. Any retained catheter bodies will be followed. Relative to the precision of the estimates with 16 subjects followed for 1 year, if the incidence of composite primary endpoint events is zero or 1, the exact upper 1-sided Clopper-Pearson 95% limit would be 17.07% and 26.40%, respectively. If the incidence of composite primary endpoint events with 26 subjects was zero or 1, the exact upper 1-sided Clopper-Pearson 95% limit would be 10.88% and 16.98%, respectively.

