A CEC will be in place for the Study using a minimum of three physicians knowledgeable in the treatment and embolization of brain AVMs. This committee will be responsible for the review and assessment of all study adverse events (AEs) that occur throughout the Study. The CEC is expected to meet each quarter at the minimum.	
Study Population:	
Subjects with a brain AVM that are indicated for AVM embolization with Onyx™ Liquid Embolic System (LES) using the Apollo™ Onyx™ Delivery Micro Catheter.	
Inclusion Criteria:	

1. The Subject or Subject's legally authorized representative has signed and dated an informed consent form.2. The Subject has a confirmed diagnosis of a brain AVM.3. The Subject is clinically and neurologically stable for a minimum of 48 hours prior to embolization.4. The Subject has a life expectancy of at least 1 year.5. The Subject agrees to and is capable of completing all study-required procedures.	
Exclusion Criteria:	

1. Current participation in another investigational drug or device study that evaluates treatments for brain AVMs or other cerebrovascular disease.2. The Subject has a bleeding disorder.3. The Subject is not a candidate for the use of vasodilators.	

PROTOCOL SYNOPSIS	
Sponsor: Micro Therapeutics, Inc. d/b/a ev3 Neurovascular [name]	Protocol Number: NV-APL001
	Revision: A, 05-Aug-2014
	Product: Apollo™ Onyx™ Delivery Micro Catheter
	Regulatory Class: Class III
	Development Phase: Phase IV
Treatment:	
An enrollment screening log will be maintained at each study site. Subjects with brain AVMs enrolled in the study will undergo embolization(s) with Onyx™ 18 LES or Onyx™ 34 LES using the Apollo™ Onyx™ Delivery Micro Catheter. Subjects may undergo multiple procedures over a several week period from the date of the initial study procedure.	
Follow-up:	
All Subjects will complete a 30-day post-embolization visit to assess safety. Once a Subject has completed the study procedures, all ongoing adverse events will be followed until resolution or until event has stabilized.	

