4.2 Number of Sites and Subjects

Up to 161 Subjects with an estimated 322 catheter utilizations (~2 catheters per Subject) will be enrolled in this study from up to 25 US sites.

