5.8 Embolization Procedure

Embolization with Onyx™ 18 LES or Onyx™ 34 LES will be performed in a neuroangiography suite using customary endovascular techniques. Intravenous sedation or general anesthesia will be used to assure Subject comfort and safety. Additional safety measures such as neurophysiological monitoring, or similar practice standards are permitted. Subjects will be heparinized, per the institutional protocol, after placement of an arterial sheath. The anticoagulation regimen and all medications used will be recorded.

The intended use of the study device and components are outlined in the IFU. Any additional pre-operative imaging and neurologic exams performed will be collected to assess changes since baseline. Table 1 describes a list of assessments that will be performed at this visit. For Subjects undergoing staged embolization procedures, data from each embolization procedure will be captured in the study electronic case report forms (eCRFs).

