9.2 Data Analysis Plan

9.2.1 General Principles

All statistical analyses will be performed using Statistical Analysis System (SAS) for Windows (version 9.2 or higher, SAS Institute Inc. Cary, NC) or other widely accepted statistical or graphical software. In general, data for all study Subjects combined will be presented. Individual data will be presented in Subject listings.

Descriptive statistics will be used to present the data and to summarize the results. Discrete variables will be presented using frequency distributions and cross tabulations. Continuous variables will be summarized by presenting the number of observations (N), mean, standard deviation, median, minimum, and maximum values.

For adverse event reporting, which includes the primary and secondary endpoints, the primary analysis will be based on Subject counts (e.g., the number and percentage of Subjects with event among the total number of Subjects). The data will be presented in the format of $p\% (x/N) [e]$, with p and x being the percentage and number of Subjects with events, respectively, N being the sample size of the analysis population, and e being the total number of events occurred in the x Subjects. For example, the data of 3.1% (5/161) [8] indicates that a total of 8 events occurred in 5 Subjects out of a total of 161 Subjects (3.1%). In addition, the data based on device (e.g., the number and percentage of devices with events among the total number of deployed devices) will also be provided.

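### The 95% exact interval for retention per deployment ignores clustering by Subject, so it is too narrow for tip retention if retention is positively correlated within Subject

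*Combined protocol and SAP*

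**What the plan says.** Section 9.2.6 (Analysis of Secondary Endpoints) plans two retention summaries. The first covers retention after any deployment, read here as a rate per Subject, with a two-sided 95% exact interval. The second takes deployments as the denominator: "catheter and tip retention by the number of deployments of the study device will be summarized using counts, percentages, and 2-sided 95% exact binomial" intervals. For this one the plan states its premise: "This tabulation assumes that each procedure / deployment is a separate trial". Repetition within a Subject is addressed only by a table: "The intra-subject rate of catheter and tip entrapment will be summarized using descriptive statistics".

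Other sections show that deployments are nested in Subjects. Section 4.2 expects up to 161 Subjects with an "estimated 322 catheter utilizations (~2 catheters per Subject"). The Treatment paragraph of the Protocol Synopsis says: "Subjects may undergo multiple procedures over a several week period from the date of the initial study procedure". Section 9.2.6 also expects that "approximately 50% to 80% of the subjects will have the tip retained by design".

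Neither the protocol nor the SAP text mentions a design effect, robust variance, GEE model or bootstrap.

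**The concern.** An exact binomial interval has its nominal coverage only if the trials are independent. Two deployments in one Subject involve the same AVM and probably the same operator's technique. Section 1.2.2 links entrapment to long injections, large reflux and vasospasm, which are features likely to recur in the same Subject. Positive correlation is therefore plausible, though the documents do not give its size.

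With positive correlation, 322 deployments carry less information than 322 independent trials, and the reported interval claims precision it does not have. Tip retention is the exposed case. It is expected to be common, and at such rates the exact method has little spare conservatism to absorb the loss. Retention per use is also a figure that a physician choosing a catheter would read directly.

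**Working it through.** **1. The plan's own exact limits.** The plan states no limit for the per-deployment interval. The only computed exact limits in section 9.2.6 are one-sided 95% Clopper-Pearson limits, upper = Beta⁻¹(0.95; x+1, n−x). For 0 and 1 events they reproduce as 17.07% and 26.40% (n = 16), and 10.88% and 16.98% (n = 26), as printed.

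**2. Inputs.** From the documents: 161 Subjects, 322 uses (322/161 = 2 each), and a tip retained in 50% to 80% of Subjects. Assumed, because the documents do not say: within-Subject correlation ρ from 0 to 0.5, and either exactly two deployments each or 1 + Poisson(1) deployments (mean 2).

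**3. Rate per deployment, p.** With two deployments, P(any retention) = 1 − [(1−p)² + ρp(1−p)]. Setting this to 0.50 and 0.80 gives p = 0.293 and 0.553 at ρ = 0, and p = 0.382 and 0.694 at ρ = 0.5. The range to examine is about 29% to 69%.

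**4. Design effect.** For equal clusters of m it is 1 + (m−1)ρ, which is 1 + ρ for pairs. For unequal clusters it is about 1 + (E[m²]/E[m] − 1)ρ. With m = 1 + Poisson(1), E[m] = 2 and E[m²] = 5, which gives 1 + 1.5ρ. As a rough guide, coverage is 2Φ(1.96/√deff) − 1. For pairs at ρ = 0.5 that is 2Φ(1.96/√1.5) − 1 = 89.0%. The exact method's conservatism adds about a point.

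**5. Coverage of the planned interval.** Beta-binomial simulation, 161 Subjects, 40,000 replicates, p from 0.29 to 0.69:

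| ρ | Two each | 1 + Poisson(1) |
|---|---|---|
| 0 | 95.4-96.3% | 95.5-95.9% |
| 0.1 | 94.2-95.3% | 93.9-94.1% |
| 0.2 | 93.1-94.1% | 92.1-92.5% |
| 0.3 | 91.8-93.1% | 90.4-90.8% |
| 0.5 | 89.6-91.1% | 87.1-87.4% |

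An exact calculation for 161 pairs agrees: averaged over rates of 25% to 80%, coverage is 95.6%, 94.5%, 93.4%, 92.2% and 90.0% at the same five correlations.

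**6. Rare events.** At 0.5% to 2% with two deployments each and ρ up to 0.3, coverage is 95.0-98.3%. With unequal numbers the protection is weaker: at 2% and ρ = 0.3 it is 93.2%. At the literature rate of 5.7% in section 9.1, with two each, it is about 94% at ρ = 0.2 and 93% at 0.3.

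**7. Worked example.** Take 80% of Subjects with a retained tip and ρ = 0.5, so p is about 69%, or 223/322. The planned interval is 63.9% to 74.3%. The effective sample size is 322/1.5 = 214.7, and Clopper-Pearson at that size gives 62.6% to 75.4%, which is 23% wider.

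**8. Does the adjusted interval work?** With the design effect estimated from the data and floored at 1, coverage is 95.4-96.4% in every cell of the table in step 5. For rates of 0.5% to 5.7%, under both deployment patterns and ρ from 0 to 0.5, it is 94.6-99.0%.

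**The case against.** The strongest reply is that the plan hides nothing. It labels the independence assumption, plans a per-Subject interval next to it, and tabulates events by number of deployments so that a reader can judge clustering. No hypothesis or performance goal uses the per-deployment interval. For adverse events and the primary endpoint, "the primary analysis will be based on Subject counts". The correlation is unknown. At 0.1 with pairs the loss is under one percentage point of coverage, and a negative correlation would make the interval too wide. The absolute change is also small: with pairs the planned half-width is 5.1 to 5.6 percentage points, and adjustment adds about 0.3 points per side at correlation 0.1 and 1.2 to 1.3 at 0.5.

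Much of this stands, and it is why the point ranks low. But disclosure does not restore coverage, the intra-subject table does not alter the interval, and the per-Subject interval answers a different question.

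Two further limits are fair. First, section 4.2 counts catheter utilizations, while section 9.2.6 speaks of a procedure or deployment. Two deployments per Subject is therefore an inference, though coverage changes little with it. Second, retention may also cluster by site or operator, since section 3.2 defines intentional detachment as a deliberate act. Under an assumed site correlation of 0.02 to 0.05 (25 equal sites, Subject correlation 0.1), the Subject-adjusted interval covers only about 90-94%. It still does better than the planned interval, but adjusting for Subject does not remove every source of dependence.

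**Conclusion.** The concern holds in its conditional form. If tip retention is positively correlated within Subject, the planned per-deployment interval covers less than its stated 95%. The shortfall is negligible at a correlation of about 0.05 or less with two deployments each, where the method's conservatism roughly offsets it. It is about 2 to 3 points at 0.3 and 4 to 5 points at 0.5 with two deployments each, and about 8 points at 0.5 when numbers vary. These sizes rest on assumed correlations and assumed cluster sizes. For rare outcomes, at 2% or less with two deployments each and correlation up to 0.3, there is no material problem.

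Clustering by Subject does not affect the primary comparison with 9.6% or the per-Subject retention interval. This is an inexpensive improvement to a descriptive secondary summary, not a threat to the trial's conclusion.

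**What to change.** In section 9.2.6, change the per-deployment retention interval only:

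- Estimate the design effect as the Subject-clustered robust variance of the retention proportion divided by the binomial variance, and set it to at least 1.
- Apply Clopper-Pearson to the events and deployments each divided by that design effect.
- With zero events, set the design effect to 1, which returns the planned interval.
- Keep the exact binomial interval for per-Subject rates.

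A GEE logistic model with robust variance, or a bootstrap that resamples Subjects, is an alternative when events are not few. Neither gives a usable interval at zero events. At a 0.5% rate, zero events occurred in 20-32% of simulated trials, and a logit interval with robust variance covered only 65-77%.

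The cost is a few lines of SAP text and code. No new data are needed, since section 5.8 already provides that "For Subjects undergoing staged embolization procedures, data from each embolization procedure will be captured in the study electronic case report forms". With two deployments each, the interval becomes about 5%, 10%, 15% and 23% wider at correlation 0.1, 0.2, 0.3 and 0.5, and about 2% wider if there is no correlation. With unequal numbers it is about 33% wider at 0.5. Fixing the method before the data are analysed avoids choosing it once the correlation can be seen.
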